## Study interventions

Children admitted into MAM or SAM treatment at the study centers will be randomized to one of three RUTF formulations:

- **Standard of care RUTF (control):** composed of milk powder, sugar, vegetable oil, peanut butter, vitamins, and minerals and low in fiber (~0.75g per 100g)
- **SMS-RUTF (intervention 1):** a milk- and peanut-free product with added crystalline amino acids that provide significantly more fiber (~5.0g per 100g)
- **S-RUTF (intervention 2):** a reduced-milk product

Burkina Faso national guidelines for MAM and SAM ambulatory treatment will be followed for dosing the products and all other aspects of treatment (4). Thus, all children will receive the standard of care for Community Management of Acute Malnutrition (CMAM) treatment in Burkina Faso, with the only difference between treatment arms being the product received. Burkina Faso national guidelines for CMAM are detailed in the guideline document (4). Briefly, upon admission to treatment for SAM, children will undergo medical evaluation and appetite test and receive routine antibiotics and rapid diagnostic test for malaria as well as other treatments as indicated in the guidelines. Caregivers of eligible children will be provided with RUTF and instructed on how to use it. Children will be followed weekly at the health center to be re-evaluated. At the follow-up visits, children's anthropometry will be measured, a clinical examination will be performed, and the caregiver will be provided with another 7-days' supply of RUTF with instructions. Children will be treated for a maximum of 12 weeks and will be eligible to be discharged when they have achieved anthropometric recovery (see definition below). For MAM, upon admission to treatment, children will be provided with RUTF to be used as a food supplement in addition to the child's usual diet. Caregivers will be provided with the product and instructed on its use and receive nutritional counseling as per guidelines. Children will receive medical treatments as indicated in the guidelines and instructed to return to the health facility every two weeks for monitoring. Children will be treated for a maximum of 12 weeks and be eligible for discharge when they have achieved anthropometric recovery.

## Study eligibility and recruitment

### Main trial

The population for this study will be children 6-59 months old with MAM or uncomplicated SAM presenting to the study facilities. MAM will be defined as mid upper arm circumference (MUAC)  $\geq 11.5$  and  $< 12.5$  cm, or weight-for-length/height z-score (WLZ/WHZ)  $\geq -3$  and  $< -2$  and absence of bilateral pitting edema. Uncomplicated SAM (i.e., cases of SAM that are eligible for ambulatory treatment) will be defined by all the following criteria: (i) MUAC  $< 11.5$  cm or WLZ/WHZ  $< -3$ , (ii) no clinical complications, (iii) absence of bilateral pitting edema, and (iv) child passes the appetite test (the child eats at least the amount of RUTF required for passing the appetite test as per Burkina Faso national guidelines (4)).

The inclusion criteria for MAM ambulatory treatment are:

- Age 6-59 months
- $11.5 \text{ cm} \leq \text{MUAC} < 12.5 \text{ cm}$ , or  $-3 \leq \text{WLZ/WHZ} < -2$
- Absence of clinical complications
- Absence of bilateral pitting edema

- Pass the appetite test
- Accompanied by caregiver or legal guardian
- Caregiver or legal guardian consents to participate

The inclusion criteria for SAM ambulatory treatment are:

- Age 6-59 months
- MUAC < 11.5 cm, or WLZ/WHZ < -3
- Absence of clinical complications
- Absence of bilateral pitting edema
- Pass the appetite test
- Accompanied by caregiver or legal guardian
- Caregiver or legal guardian consents to participate

The exclusion criteria for MAM or SAM ambulatory treatment are therefore:

- Acute malnutrition requiring hospitalization (presence of clinical complications, failure to pass the appetite test, or presence of bilateral pitting edema)
- Known allergy to any of the ingredients in the RUTF products
- Already enrolled in MAM or SAM ambulatory treatment program
- Presence of physical abnormalities that make measurement of anthropometry impossible
- Caregiver has intention to move out of the study area within the next 6 months

Children will be screened for eligibility upon presentation at the study health centers, and will be determined to be eligible upon diagnosis with uncomplicated MAM or SAM.

#### Sub-study 1: Acceptability

This nested sub-study will recruit children with MAM at a sub-set of 5 of the 30 study facilities in the main trial. Inclusion criteria for this sub-study therefore include age 6-59 months, MUAC < 125 mm and  $\geq 115$  mm, or WLZ/WHZ < -2 and  $\geq -3$ , absence of clinical complications, passing the appetite test, accompanied by caregiver or legal guardian, and caregiver consent. Exclusion criteria include presence of SAM, requiring hospitalization, known RUTF ingredient allergies, already enrolled in a MAM or SAM treatment program, physical abnormalities that cause measurement issues, or plans to move away within six months.

#### Sub-study 2: Microbiome and gut health

This nested sub-study will recruit children with SAM at a sub-set of 5 of the 30 study facilities in the main trial. Inclusion criteria for this sub-study therefore include age 6-59 months, MUAC < 115 mm or WLZ/WHZ < -3, absence of clinical complications, passing the appetite test, accompanied by caregiver or legal guardian, and caregiver consent. Exclusion criteria include needing hospitalization, known RUTF ingredient allergies, already enrolled in a MAM or SAM treatment program, physical abnormalities that cause measurement issues, or plans to move away within six months.

### Sub-study 3: Costing

This nested sub-study will have the same population as the main trial, i.e., children 6-59 months old with MAM or uncomplicated SAM presenting to the study facilities. In all study facilities, we will observe at least one visit for a child at each of the 30 study facilities for documenting staff time allocations. We will collect caregiver cost information from the caregivers participating in the acceptability sub-study.

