Personnel	Salaries of health workers involved in the admission, follow up, and discharge of outpatient SAM children
Overheads	Costs of infrastructure, management, administration, and logistical support

Data sources will include accounting records and interviews. We will collect accounting data from the study hospitals that cover the time period of interest, which will provide an exhaustive list of inputs and materials and support used in the program. We will conduct interviews with staff members and other key actors involved in the treatment of SAM, and the management and logistical support. A subset of caregivers will be interviewed about their direct, indirect, and opportunity costs for the admission visit as part of the baseline questionnaires, and will be asked about these costs for the follow-up visits and discharge visit at the discharge visit.

Costing data from accounting records and interviews will be entered into Excel spreadsheets, which will be used for the analysis. Data be securely stored on password-protected computers and on secure servers.

We will estimate total costs, and the cost-efficiency and cost-effectiveness of the intervention. Cost-efficiency refers to the estimates of cost per programmatic output, allowing for the comparison of programs that produce the same output. Cost-effectiveness refers to cost per health outcome, allowing an assessment of value-for-money of a health intervention given its health impacts. All outcomes are defined in Table 6.

If the interventions are demonstrated to be superior for relapse, we will calculate the cost per DALY averted between each intervention arm and the control. To do this, we will construct a decision tree model to compare the costs and effects of treatment with the intervention RUTFs relative to standard RUTF. The health states that will contribute to DALYs are SAM and death. The effects of the intervention package will include effects on relapse. Disability weights will be sourced from the most recently published Global Burden of Disease disability weight estimates. We will not employ age-weighting and discounting (29). Both probability and deterministic sensitivity analyses will be conducted. If the interventions are demonstrated to be non-inferior for both recovery and relapse outcomes, we will calculate the difference in costs between each intervention arm and the control.

All analyses will be conducted using TreeAge, Excel, and Stata software.

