#### Sub-study 1: Acceptability

In a sub-set of facilities, we will conduct a 3x3 full Latin square crossover design to evaluate acceptability of the two products to address objective 1 (acceptability of S-RUTF and SMS-RUTF) and assess the adaptation to the products to address objective 2 (sensory adaptation). The 3x3 full Latin square crossover design will involve measurements of the RUSFs' observed intakes at four time points — baseline (day 1), day 8 (product switching), day 15 (product switching), and day 22.

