#### Sub-study 3: Costing

We will employ an activity-based costing-ingredients (ABC-I) approach to collect and analyze data on costs incurred in each treatment arm. This approach involves documenting all costs and allocating them to the activity in which they were incurred. Both societal and health system perspectives will be used. The health system perspective includes only costs to the health system, whereas the societal perspective includes health system costs as well as expenses and opportunity costs to caregivers (2,3). This will include costs and opportunity costs to caregivers.

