### Sub-study 1: Acceptability

A total sample size of 102 children was targeted based on recommendations in UNICEF protocols for acceptability testing of novel RUTF products, the requirement for complete sequences in a 3×3 full Latin square crossover design, and statistical power considerations. The sample size is consistent with the statistical power considerations, assuming a non-inferiority margin of 4 grams per observed intake in 30 minutes from a test dose, a between-subject standard deviation (SD) of 6.75 grams per kilogram body weight from literature, a conservative intra-class correlation (ICC) of 0.3, and an overall alpha (two-sided) of 0.05 (translating to a one-sided alpha of 0.025 for a non-inferiority test), 90% power, and attrition rate of 20%.

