### Sub-study 3: Costing

As the goal of the costing study is descriptive and no statistical hypothesis testing will be conducted, the sample size is not based on statistical power calculations. Rather the sample size is based on concerns of feasibility and representativeness of the sample. The selected sample size is expected to lead to costing results that are representative of the costs for MAM and SAM treatment in these 30 health facilities and will be feasible to collect.

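### The only caregiver-cost source the SAP names observes no SAM caregivers and no course on a single randomised product, and it differs from the Protocol

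*SAP*

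**What the plan says.** **Source of caregiver costs.** Under Study eligibility and recruitment, Sub-study 3: Costing, the SAP gives the costing work the main-trial population, MAM and SAM. It then states: "We will collect caregiver cost information from the caregivers participating in the acceptability sub-study". No other source of caregiver costs appears in the SAP.

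**What that sub-study is.** Its eligibility section says "This nested sub-study will recruit children with MAM at a sub-set of 5 of the 30 study facilities in the main trial", and adds "Exclusion criteria include presence of SAM". The design section describes a three-product crossover with intake measured at "baseline (day 1), day 8 (product switching), day 15 (product switching), and day 22". The sample size section says "A total sample size of 102 children was targeted". The footnote to SAP Table 8 adds that a child who progresses to SAM is withdrawn from the sub-study.

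**What the costing is meant to deliver.** The SAP design section for costing says it will "collect and analyze data on costs incurred in each treatment arm", from both a health-system and a societal perspective, the latter including what caregivers spend and the value of their time. Table 3 lists separate cost outcomes for MAM and SAM, per admission and per recovery. Table 10 defines indirect costs as those falling on caregivers because of SAM treatment. The sample size section expects results "representative of the costs for MAM and SAM treatment in these 30 health facilities".

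**The Protocol.** Its Costing section plans otherwise: "A subset of caregivers will be interviewed about their direct, indirect, and opportunity costs for the admission visit as part of the baseline questionnaires". Costs of the follow-up and discharge visits are asked about at discharge. Protocol Table 7 lists caregiver costing questions, for a subset, in the main study schedule. The Protocol's own acceptability sample is 40 SAM and MAM children in two feeding sessions, and nothing links it to the costing subset.

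**The concern.** The societal perspective differs from the health-system perspective only by the caregiver component. If that component comes from a MAM-only crossover, the societal cost per SAM child rests on caregivers who were never observed, and no caregiver in the data belongs to a randomised arm. The SAP gives no rule for carrying crossover costs over to an arm, to SAM or to a full treatment course, and it claims a representativeness that this source cannot supply.

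At stake are the societal versions of the SAM cost outcomes and of any cost difference between products. The latter includes the cost per DALY averted that the SAP plans if superiority is shown, should it be reported from the societal perspective.

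**Working it through.** The SAP states that the costing sample has no power basis, so there is no planned figure to reproduce. The check is a comparison of sections plus visit arithmetic.

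**1. Promise against source (caregiver component only)**

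| SAP commitment | What the crossover supplies |
|---|---|
| Costs by treatment arm (Study design, Sub-study 3) | No child on one product for a course; products switch on days 8 and 15 |
| SAM cost per admission and per recovery (Table 3) | 0 SAM caregivers; 1080 SAM children are planned in the main trial |
| Caregiver costs of SAM treatment (Table 10) | 0 SAM caregivers |
| Representative of MAM and SAM in 30 facilities (Sample size, Sub-study 3) | Up to 102 MAM children at 5/30 = 17% of facilities |

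**2. Does a crossover total stand for a treatment course?**

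Inputs: SAP Table 4 lengths of stay (MAM 36.4 days, SAM 56 days), the 12-week (84-day) maximum, and visits every 14 days for MAM and every 7 days for SAM. Assume every scheduled visit is attended.

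Visits = 1 (admission) + length of stay / visit interval

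- MAM: 1 + 36.4/14 = 3.6; at the maximum, 1 + 84/14 = 7
- SAM: 1 + 56/7 = 9; at the maximum, 1 + 84/7 = 13
- Crossover: days 1, 8, 15 and 22, so 4 visits over 21 days for every child who completes it

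The crossover count lies close to the average MAM course, but it is fixed by design and so cannot follow length of stay. It is 4/9 = 44% of the average SAM course. What the sub-study can supply is a cost per visit.

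**3. How much do arm-specific visit counts matter?**

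Take the length-of-stay margins in SAP Table 4 as an illustrative difference between arms, and hold cost per visit constant.

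- SAM: 8 days / 7 = 1.1 extra visits; 1.1/9 = about 13% of caregiver visit cost
- MAM: 4.9 days / 14 = 0.35 extra visits; 0.35/3.6 = about 10%

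Differences of this size appear if the cost per visit is multiplied by visits recorded in each arm. They disappear if one crossover-based figure per child is applied to all arms. The SAP does not say which will be done.

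**4. SAP against Protocol**

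The Protocol's subset is questioned about admission, follow-up and discharge visits within the main schedule. The SAP's caregivers come from a separate three-week crossover. The SAP does not explain the change or say whether the Protocol's questions were kept. The Protocol does not say that its subset spans arms or severity strata.

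**The case against.** Several stronger readings are tempting, and the documents do not support them.

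- **That the trial cannot give caregiver-inclusive costs by product or for SAM.** The Protocol schedules caregiver cost questions in the main study, and the SAP does not expressly withdraw them. Attendance and length of stay are main-trial outcomes, so a cost per visit can be combined with visits by arm. For SAM this needs one further assumption: that a visit costs a SAM caregiver what it costs a MAM caregiver.
- **That longer stays on one product would be invisible in caregiver cost.** The main trial records length of stay by randomised arm. Only a product difference in cost per visit would be missed, and the documents give no reason to expect travel or food costs to depend on the sachet received.
- **That MAM caregiver costs will be overstated because crossover visits are weekly.** Nothing in the SAP plans to sum crossover visits into a course cost, and weekly visits are the routine SAM interval.
- **That research time is counted as caregiver cost.** Table 10 values time spent having the child treated for wasting. The questionnaire is not described, so inclusion of the observed-feeding time is a risk, not a fact.

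Importance is also limited. Costing is a secondary, descriptive objective, and the Protocol's economic case rests mainly on product cost (milk 25% and peanuts 15% of it). Product and health-system costs remain available by arm and for SAM.

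All of this narrows the point. It does not supply the missing SAM caregivers or the missing extrapolation rule, and it does not make the representativeness statement true of caregiver costs.

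**Conclusion.** The point holds in this form. The only caregiver-cost source named in the SAP gives no directly observed caregiver cost for SAM or by randomised arm, while the SAP commits to both and claims representativeness for MAM and SAM at 30 facilities. For the caregiver component the coverage is 0 SAM caregivers, up to 102 MAM caregivers and 5 of 30 facilities. The SAP also departs from the Protocol without explanation.

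The defect is an unstated extrapolation and an inaccurate claim, confined to the caregiver part of the societal perspective. It should be corrected. It does not touch the efficacy analyses.

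The conclusion assumes that the SAP's silence means no other caregiver data are planned. If the Protocol's questions were in fact put to main-trial caregivers, the remedy is largely one of wording. The visit counts and percentages in the working rest on the SAP's literature-based lengths of stay and on full attendance.

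**What to change.** First, reconcile the SAP sentence with the Protocol's Costing section and Table 7, and state what caregiver data were actually collected.

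- **If main-trial caregiver data exist or can still be collected**, use them, and require that they cover MAM and SAM and all three arms. This goes further than the Protocol's unspecified subset. The SAP's Statistical methods section refers in the past tense to children enrolled near the end of the study, so new collection may no longer be feasible.
- **Otherwise**, state that the sub-study supplies only a caregiver cost per visit (transport, food, travel and routine visit time), excluding any observed-feeding time. Multiply it by the visits recorded for main-trial children, by arm and by MAM or SAM. Label the SAM unit cost as borrowed from MAM caregivers at 5 facilities, and vary it in sensitivity analysis. An error in that unit cost carries through to the SAM caregiver component in full proportion.

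Under the second option, remove the representativeness claim for caregiver costs in the SAP's costing sample size section. Under the first, limit it to what the data cover.

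Cost: a SAP wording change and a modest recalculation from visit data the main trial already records. The downside is a little more analysis and a less favourable statement about representativeness.

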### Study ethics summary

The study protocol was approved by the Institutional Review Boards (IRBs) of IFPRI (Washington DC, USA), and the Burkina Faso National Ethics Committee. The study was registered on [clinicaltrials.gov](https://clinicaltrials.gov) (identifier: NCT06912620). Caregivers or legal guardians of eligible children will undergo informed consent, and all participant data will be collected and stored confidentially. All sub-studies were included in the main study protocol.

### Controls

#### Blinding

This study will be triple blinded; that is, the study investigators, participants, and outcome data collectors will be blinded to randomization assignment. The study products will have identical packaging, and will be stored in boxes that are identically labeled to the extent possible. The products will be identified only with one of three alphabet letters, and the codes to these alphabet letters will not be accessible by the study team until after analyses are completed. While the participants will technically be blinded to their treatment assignment, the products will likely differ in their taste and appearance, meaning that true blinding for participants may not be possible due to the nature of their different recipes. However, we expect concerns of bias due to this to be minimal.

#### Method of treatment assignment/randomization

A statistician who is not part of the research team will generate a randomization scheme for the allocation of the 3 supplements. Each unique randomization number is randomly allocated to 1 of 9 letter codes (e.g., A, E, I, Z, K, T, N, E, S)—3 letters for the SMS-RUTF supplement, 3 letters for the S-RUTF supplement and 3 letters for the standard RUTF (control group)—using a computer program in blocks of 45. Without the investigators' knowledge, the producers will be informed which letters to print on the package of each supplement. Information regarding the assignment of the letter codes to the intervention and control supplements will be stored electronically by the director of Nutrition, Diets and Health unit of IFPRI, inaccessible by the investigators, until analysis is completed.

Eligible children will be randomly assigned to one of the three study groups at study inclusion. The study staff will open the sealed envelope corresponding to the next sequential participant identification number in the presence of an eligible mother-child pair (in order of arrival) and will provide them with the RUTF supplement according to the letter code. The participant's number, as well as the letter code, will be recorded on the study participant's card, their medical records, and scanned into the electronic data capture system.

## Study outcomes

### Main trial

The primary and secondary outcomes for the main trial and their definitions are listed in Table 1. Outcomes are the same for MAM and SAM children.

*Table 1. Primary and secondary efficacy outcomes*

Outcomes	Definition	Type of analysis
Primary outcomes		
Anthropometric recovery at discharge	WLZ $\geq$ -2 and MUAC $\geq$ 125 mm and absence of bilateral pitting edema for two consecutive visits, at the day of end of treatment	Non-inferiority
Relapse to wasting within 3 months post-discharge	A new episode of wasting (defined as WLZ/WHZ $<$ -2 or MUAC $<$ 125 mm or presence of bilateral pitting edema) within the 3-month period following recovery from the index wasting episode, among children who recovered from their index episode	Superiority
Length of stay (LOS) among recovered children	The number of days between the day the child is admitted to treatment and the day the child is determined to be recovered and thus discharged from treatment	Non-inferiority
Weight gain	Change in child's weight (gram/kilogram/day) between weight on day of admission to treatment and the day of end of treatment	Non-inferiority
Anthropometry at discharge from treatment	WLZ/WHZ, MUAC, weight, height/length, LAZ/HAZ and WAZ at the day of end of treatment	Non-inferiority
Anthropometry at 3-months post-discharge	WLZ/WHZ, MUAC, weight, height/length, LAZ/HAZ and WAZ at 3-months post-discharge (3 months after the day of end of treatment)	Superiority
Hemoglobin at discharge	Hemoglobin concentration (grams/liter) at the day of end of treatment	Non-inferiority
Hemoglobin at 3-months post-discharge	Hemoglobin concentration (grams/liter) at 3-months post-discharge (3 months after the day of end of treatment)	Superiority
Secondary outcomes		
Default from treatment	Child is absent for two consecutive visits, declared a defaulter on the second visit	Non-inferiority
Transfer to inpatient treatment	Referral or admission to hospital for inpatient treatment during the treatment course. As per the Burkina Faso national protocol, children are to be transferred to inpatient care if they meet any of the following criteria: negative appetite test, weight loss for 3 consecutive visits, stagnant weight for 4 consecutive visits if all other social and nutritional reasons have been addressed, onset of clinical condition (edema, fever, hypothermia, severe dehydration, repeated or incessant vomiting, severe respiratory problem, very pale with difficulty breathing, severe malaria,	Non-inferiority

	abscesses or extensive skin lesions, weakness or unconsciousness, convulsions or malaise) (4).	
Non-response to treatment	Any of the following criteria are met: Absence of weight gain after 5 weeks or at the third visit; weight loss for more than 4 weeks in the program or at the second visit; loss of more than 5% of body weight compared to admission weight at any time; or anthropometric recovery criteria not met after 3 months of follow-up in CMAM. Children who are non-responders are referred to inpatient care as per Burkina Faso guidelines.	Non-inferiority
Adherence to treatment services	Caregiver attends the recommended schedule of visits and receive RUTF supply	Non-inferiority
Relapse to SAM	A new episode of SAM (WLZ/WHZ < -3 or MUAC < 115 mm or presence of bilateral pitting edema) within the 3-month period following recovery from the index wasting episode	Superiority
Relapse to MAM	A new episode of MAM (WLZ/WHZ < -2 and $\geq$ -3, or MUAC < 125 mm and $\geq$ 115 mm) within the 3-month period following recovery from the index wasting episode	Superiority
Morbidity signs or diagnoses	Indication of morbidity on health center card	Non-inferiority
Anemia at discharge	Hemoglobin concentration < 105 gram/liter for children 6-23 months of age or < 110 gram/liter for children 24-59 months of age, at discharge	Non-inferiority
Anemia at 3-months post-discharge	Hemoglobin concentration < 105 gram/liter for children 6-23 months of age or < 110 gram/liter for children 24-59 months of age, at 3-months post-discharge	Superiority
Mortality	Death at any time during treatment or during the post-discharge follow-up period	Non-inferiority

